#### **6.3.2** Adverse Events

All AEs will be collected after the participant signs the informed consent. AEs will be characterized by seriousness, special interest, severity, relationship to study drug, and outcome.

AEs will be collected and coded by system organ class (SOC) and PT using MedDRA, Version 23 or newer.

#### **6.3.2.1** Treatment-Emergent Adverse Events

- If both the start time of the AE and the time of the first study drug administration are available, an AE is considered a TEAE if its start date and time are after the first study drug administration start time and no later than 90 days after the last dose date. The last dose date is defined in Section 7.1.1.1.
- If either the start time of the AE or the time of the first study drug administration is unavailable, an AE is considered a TEAE if its start date is on or after the first dose date and no later than 90 days after the last dose date. Handling of incomplete dates is specified in Section 6.3.2.6.

Protocol No. AL002-2 Last Revision Date: 12 Aug 2025

### **6.3.2.2** Adverse Events of Special Interest

An AE of special interest (AESI) is a serious or nonserious AE that is of scientific and medical concern specific to a product for which ongoing monitoring and rapid reporting by the Investigator to the Sponsor should occur. AESI for this study are defined as the following occurrences:

- Amyloid-related imaging abnormality hemosiderin deposits (ARIA-H)
- Amyloid-related imaging abnormality edema (ARIA-E)
- Uveitis Grade 2 or higher

#### **6.3.2.3** Serious Adverse Events

SAEs will be identified and captured as SAEs if AEs met the definitions of SAEs that were specified in the protocol.

#### 6.3.2.4 Relationship of Adverse Events to Study Drug

Related AEs are those for which the Investigator selected "Related" on the AE electronic CRF to the question whether an event is related to study drug. Relatedness will always default to the Investigator's choice, not that of the medical monitor.

#### 6.3.2.5 Relationship of Adverse Events to Radiotracers

A listing will be provided for TEAEs that are related to radiotracers.

### **6.3.2.6 Incomplete Dates**

If the start date of the AE is incomplete and the AE end date is not prior to the first dose date of study drug, then the month and year (or year alone if month is not recorded) of onset determine whether an AE is treatment emergent. The event is considered treatment emergent if both of the following 2 criteria are met:

- The AE start date is the same as or after the month and year (or year) of the first dose date of study drug, and
- The AE start date is the same as or before the month and year (or year) of the date corresponding to 90 days after the date of the last dose of study drug.

An AE with completely missing start and end dates, or with the start date missing and an end date later than the first dose date of study drug, will be considered treatment emergent. In addition, an AE with the start date missing and incomplete end date with the same or later month and year (or year alone if month is not recorded) as the first dose date of study drug will be considered treatment emergent.

An imputation will be done for partial dates in order to compute an estimated study day for display in the listing. For partial start date:

- If the year is unknown, then the date will be assigned the first dose date.
- If the month is unknown, then:
  - a) If the year matches the year of the first dose date, then the month and day of the first dose date will be imputed.
  - b) Otherwise, 'January' will be assigned.

Protocol No. AL002-2 Last Revision Date: 12 Aug 2025

- If the day is unknown, then:
  - a) If the month and year match the month and year of the first dose date, then the day of the first dose date will be imputed.
  - b) Otherwise, '01' will be assigned.

#### For partial end date:

- If the year is unknown, then the date will be assigned the last visit date.
- If the month is unknown, then:
  - a) If the year matches the year of the last visit date, then the month and day of the last visit date will be imputed.
  - b) Otherwise, "December" will be assigned.
- If the day is unknown, then:
  - a) If the month and year match the month and year of the last visit date, then the day of the last visit date will be imputed.
  - b) Otherwise, the last day of the month will be assigned.

The last visit date is the date of last visit (any scheduled, unscheduled, ET, EFU, or SFU visit) during the study.

If the imputation takes the start date past the known end date, then the start date will be set to the day before the end date. If the imputation takes the end date prior to the known start date, then the end date will be set to the day after the start date.

#### **6.3.2.7** Deaths

Deaths will be captured as SAEs (i.e., SAEs result in death regardless whether it is treatment-emergent or not) according to the methods described above.

#### 6.3.3 Columbia-Suicide Severity Rating Scale (C-SSRS)

Two versions of the C-SSRS will be used in this study: a Screening/Baseline version and a Since Last Visit version. The Screening/Baseline version of the C-SSRS assesses the lifetime suicidal ideation and behavior and non-suicidal self-injurious behavior, the suicidal ideation in the past 6 months and suicidal behavior and non-suicidal self-injurious behavior in the past 2 years. The Screening/Baseline version of the C-SSRS will be administered on Study Day 1 prior to dosing. The Since Last Visit version of the C-SSRS assesses suicidal thoughts or behaviors the participant may have had since the last time the C-SSRS was administered as specified in the Schedules of Assessments in the protocol.

#### 6.3.4 Laboratory Data

Collection schedule for hematology, blood chemistry, urinalysis testing, and coagulation are specified in the Schedules of Assessments in the protocol.

Indicators of values below or above a limit of quantitation (the lower limit of quantitation (LLOQ) or the upper limit of quantitation (ULOQ)) will be included, as well as all LLOQ or ULOQ limits. When values

Protocol No. AL002-2 Last Revision Date: 12 Aug 2025

are below or above a limit of quantitation, they will be listed as such, and the closest imputed value will be used for calculating summary statistics as specified in Section 7.1.4.

The tests performed are shown below in Table 6-3.

#### 6.3.4.1 Conversion to the International System of Units

All laboratory data will be stored in the database with the units in which they are originally reported. Laboratory data in summary tables and by-participant data listings will be presented in the International System of Units (SI units; Système International d'Unités). Laboratory data not reported in SI units will be converted to SI units before further processing or data analysis, unless otherwise specified.

**Table 6-3. Clinical Laboratory Safety Assessments** 

Test	Analytes
Hematology	Absolute neutrophil count, hemoglobin, hematocrit, MCH, MCV, MCHC, white blood cells, red blood cells, platelet count, and differential count (neutrophils, lymphocytes, monocytes, basophils, eosinophils).
Chemistry (serum or plasma)	Sodium, potassium, chloride, calcium, glucose, bicarbonate, albumin, total protein, creatinine, HbA1C, blood urea nitrogen or urea, aspartate aminotransferase, alanine aminotransferase, gamma glutamyl transpeptidase, alkaline phosphatase, phosphorous, total bilirubin (direct and indirect), amylase, cholesterol (total, LDL, HDL), triglycerides, uric acid, creatine phosphokinase, lactate dehydrogenase, magnesium, C-reactive protein.  Thyroid-stimulating hormone, folic acid, vitamin B12, and viral serology (HIV-1 or HIV-2 antibody and antigen, hepatitis B surface antigen, total hepatitis B core antibody, HCV antibody/RNA) will also be assessed at screening only.
Coagulation	Prothrombin time with INR, activated partial thromboplastin time
Urinalysis	Dipstick (pH, specific gravity, glucose, protein, ketones, blood). Microscopic analysis in the event of abnormal dipstick results (urinary sediment, red blood cells, white blood cells, casts, crystals, epithelial cells, bacteria).

Abbreviations: HbA1C =hemoglobin A1C; HCV=hepatitis C virus; HDL=high density lipoprotein; HIV=human immunodeficiency virus; INR=international normalized ratio; LDL=low density lipoprotein; MCH=Mean Corpuscular Hemoglobin; MCHC=Mean Corpuscular Hemoglobin Concentration; MCV=Mean Corpuscular Volume; WOCBP=woman of childbearing potential.

#### 6.3.4.2 Potential Serious Hepatotoxicity

Following Hy's law, potential serious hepatotoxicity is defined as ALT or AST > 3 x ULN and total bilirubin > 2 x ULN at any time post-baseline, not necessarily concurrent.

#### 6.3.5 Electrocardiogram (ECG)

Triplicate 12-lead ECGs including heart rate, QRS duration, QT interval corrected using the Fridericia formula (QTcF) interval, RR interval and result interpretation will be captured on the electronic CRF. Triplicate 12-lead ECGs will be obtained approximately 1 minute apart at the Screening and before blood draws (predose) and 60 to 90 minutes after the end of infusion at scheduled visits (refer to the protocol for scheduled visits). The investigator will assess and

Protocol No. AL002-2 Last Revision Date: 12 Aug 2025

document whether the ECG is "Normal", "Abnormal not clinically significant", "Abnormal clinically significant" or "Not evaluable". In addition, triplicate ECG tracings from Day 1 and Week 25 or Week 49 for approximately 100 consecutive participants will be read by a core ECG laboratory. Results from centrally read ECGs will not be captured on the electronic CRF but provided by a vendor and will be analyzed separately.

ECG parameters will include the following:

- Heart Rate (beats/min)
- QRS duration (msec)
- RR Interval (msec)
- QTcF Interval (msec)
- Interpretation

#### 6.3.6 Vital Signs

Vital signs (supine systolic blood pressure, diastolic blood pressure, pulse rate, respiratory rate, and temperature) will be measured at all visits. Height will be collected at Screening. Weight will be collected at scheduled visits (refer to the protocol for scheduled visits).

Vital signs parameters will include the following:

- Weight (kg)
- Systolic Blood Pressure (millimeter of mercury (mmHg))
- Diastolic Blood Pressure (mmHg)
- Pulse Rate (beats/min)
- Respiratory Rate (breaths/min)
- Temperature (C)

#### 6.3.7 Magnetic Resonance Imaging (MRI) for Detection of ARIA-E and ARIA-H

Brain MRI will be performed to detect brain abnormalities, such as ARIA-E and ARIA-H.

#### 6.3.7.1 ARIA-E

#### 6.3.7.1.1 Event Definition

An event of ARIA-E is defined as an MRI scan where the brain MRI worksheet (BMW) shows the presence of vasogenic edema.

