7.11. Amyloid-Related Imaging Abnormalities

Amongst the brain abnormalities detected on MRI are ARIA which are believed to reflect leakage of proteinaceous fluid or other blood products into the leptomeninges or brain parenchyma. The term ARIA was originally coined to describe specific brain abnormalities seen on MRI in anti-amyloid clinical trials. Although MRI findings potentially caused by AL002 may or may not be related to disruption/mobilization of, or a reaction to, amyloid species in the brain parenchyma or vasculature, the term ARIA will be used in this protocol to describe such findings until the biological mechanism is better understood. Specifically, according to the convention developed to describe ARIA occurring in clinical trials of anti-amyloid immunotherapies, ARIA-E will refer to MRI findings of vasogenic edema and leptomeningeal/sulcal effusion, and ARIA-H will refer to MRI findings of cerebral microhemorrhages, leptomeningeal hemosiderosis (also known as superficial siderosis of the CNS) and cerebral macrohemorrhages.

For the purpose of this protocol, four categories of ARIA will be tracked (see Section 7.2.1 for recording of AESIs of ARIA). These categories are ARIA-E, ARIA-H cerebral microhemorrhages, ARIA-H leptomeningeal hemosiderosis, and ARIA-H cerebral macrohemorrhages. Symptoms associated with ARIA-H and ARIA-E will be captured as separate AEs on the AE eCRF and linked to the applicable ARIA AE line number. All clinical signs and symptoms that are identified as associated with an ARIA finding will be entered as separate AEs on the AE eCRF. Based on evaluation of the participant for signs and symptoms, and review of safety findings by the Sponsor that possibly indicates the presence of ARIA, the Sponsor may request an unscheduled MRI be obtained.

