To maintain consistency of reporting across clinical sites, findings of ARIA-E or ARIA-H on MRI are determined by the MRI Central Reader by radiologists with expertise in assessing for ARIA and other abnormalities on brain MRI. ARIA-E, ARIA-H and other findings are documented on and reported to the sites with the BMW report (see Section 6.5.12). The BMW provided by the Central Reader after each MRI examination scores ARIA-E (parenchymal vasogenic edema, leptomeningeal/sulcal effusion) according to: extent, location, number of sites involved, radiographic severity (mild, mild+, moderate, moderate+, severe) (Table 6) and changes since prior MRI exams. ARIA-E findings typically resolve radiographically and will be noted as such on the BMW of follow-up MRI scans. The BMW also documents occurrence and characteristics (location, size, number) of ARIA-H (parenchymal microhemorrhages and leptomeningeal hemosiderosis and macrohemorrhages).

Overall, ARIA-H radiographic severity is defined as the worst individual radiographic severity for microhemorrhages, leptomeningeal hemosiderosis or macrohemorrhages (eg, if there are

Alector, Inc.

4 incident microhemorrhages, 1 incident areas of leptomeningeal hemosiderosis and no macrohemorrhages, then ARIA-H is rated as "Moderate") (Table 6).

Table 6: ARIA-E and ARIA-H Radiographic Severity Scales

ARIA-E Characterization:		Severity/Grade	
<5 cm monofocal		Mild (Grade 1)	
<5 cm multifocal		Mild+ (Grade 2)	
5-10 cm monofocal	N	Moderate (Grade 3)
5-10 cm multifocal	Moderate+ (Grade 4)		
>10 cm monofocal/multifocal	Severe (Grade 5)		
Incident ARIA-H:	Mild	Moderate	Severe
microhemorrhages	1-4	5-9	10 or more
Areas of leptomeningeal hemosiderosis	NA	1	2 or more
macrohemorrhages	NA	NA	1 or more

ARIA-E=amyloid-related imaging abnormalities-edema; ARIA-H=amyloid-related imaging abnormalities-hemosiderin deposits; NA=not applicable.

ARIA-H findings very rarely resolve radiographically; it is more typical for ARIA-H findings to stabilize radiographically. Radiographic stabilization of an ARIA-H finding is defined as when a follow-up MRI scan shows no increase in number/size/extent of previously seen cerebral microhemorrhages, leptomeningeal hemosiderosis and cerebral macrohemorrhages.

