#### 6.3.7.1.2 Severity Definition

ARIA-E severity is based on radiographic severity as captured on BMWs.

Protocol No. AL002-2 Last Revision Date: 12 Aug 2025

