## 6.3.7.1.3 Resolution and Time to Resolution Definition

- ARIA-E is considered resolved for a participant if all the subsequent MRI scans showed no ARIA-E following the last MRI scan showing ARIA-E.
- Time to resolution is defined as the number of days from the exam date of the first MRI scan showing ARIA-E to the exam date of the earliest MRI showing no ARIA-E after the last one showing ARIA-E. If a participant had a resolved but recurrent ARIA-E after the previous one was resolved, both times to resolution are included.

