## 6.3.7.1.4 Time to First Occurrence and Recurrence Definition

- Time to the first occurrence is defined as the number of days from the first dose date to the exam date of the first MRI scan showing ARIA-E.
- For a participant, if there was an MRI scan showing ARIA-E, followed by a subsequent MRI scan not showing ARIA-E, followed by a subsequent MRI scan again showing ARIA-E, this participant is considered to have a reoccurrence of ARIA-E.

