## 7.5.7 Magnetic Resonance Imaging (MRI) for Detection of ARIA-E and ARIA-H

Incidence of the first occurrence of ARIA-E within each post-baseline visit will be summarized by radiographic severity for each visit (refer to Table 7-9 for analysis visit window definition) and overall during the treatment period. The same incidence table will be summarized for post-baseline new ARIA-H. In addition to radiographic severity for ARIA-H, individual radiographic severity for microhemorrhages, leptomeningeal hemosiderosis, and macrohemorrhages for the first occurrence of new ARIA-H will also be summarized by visit and overall during the treatment period.

Incidence of any occurrence of ARIA-E within each post-baseline visit will be summarized in the same fashion. In the case of multiple values in the baseline analysis visit window, the rules described in the Section 7.1.3.2 still apply. In the case of multiple values in a post-baseline analysis visit window, the

Protocol No. AL002-2 Last Revision Date: 12 Aug 2025

rules described in the Section 7.1.3.2 do not apply to this summary, but the worst-case scenario will be applied as below:

- A participant having a record indicating no ARIA-E and a different record indicating ARIA-E is considered experienced ARIA-E per visit or overall.
- A participant having experienced ARIA-E more than once per visit or overall is counted once in the number of participants with ARIA-E per visit or overall.
- The maximum severity is selected if ARIA-E was observed more than once for a participant per visit or overall post-baseline.

The same incidence table will be summarized for post-baseline new ARIA-H. In the case of multiple values in an analysis visit window, the same rules described above apply. In addition to radiographic severity for ARIA-H, individual radiographic severity for microhemorrhages, leptomeningeal hemosiderosis, and macrohemorrhages for the any occurrence of new ARIA-H will also be summarized by visit and overall during the treatment period. The maximum severity of ARIA-H is selected for a participant per visit or overall post-baseline, and the individual radiographic severity corresponding to the selected ARIA-H will be summarized per visit or overall post-baseline.

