APOE genotype, time to the first occurrence, resolution, time to resolution, and reoccurrence will be summarized for participants with ARIA-E. APOE genotype and time to the first occurrence will be summarized for participants with post-baseline new ARIA-H.

The number and percentage of participants who had a post-baseline ARIA-E but did not have a new ARIA-H any time post-baseline will be summarized. The number and percentage of participants who had a new ARIA-H but did not have an ARIA-E any time post-baseline will be summarized. Similarly, the number and percentage of participants who had a new ARIA-H and an ARIA-E any time post-baseline will be summarized.

All the MRI summaries described above will also be provided separately for participants with the following APOE genotype(s) (1) e4/e4, (2) e4 carriers (including e2/e4, e3/e4 and e4/e4), (3) non-e4 carriers (excluding e2/e4, e3/e4 and e4/e4), and (4) e4 heterozygous carriers (including e2/e4 and e3/e4).

The Kaplan-Meier curve for the time to the first occurrence of ARIA-E will be plotted. For participants experienced at least one ARIA-E, the time to the first occurrence of ARIA-E is the time from the first dose date to the onset date of the first ARIA-E occurrence. For participants who did not experience ARIA-E, the censor date will be the earlier date of the last MRI scan date and the last dose date plus 90 days. Similarly, the Kaplan-Meier curve for the time to the first occurrence of new ARIA-H will be plotted.

All MRI findings will be listed.

Protocol No. AL002-2 Last Revision Date: 12 Aug 2025

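### The SAP's ARIA-E event rule names vasogenic edema only, whereas the protocol also includes leptomeningeal/sulcal effusion, and the narrower rule is not declared

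*SAP*

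**What the plan says.** **Protocol.** Section 7.11 sets the meaning of the term: "ARIA-E will refer to MRI findings of vasogenic edema and leptomeningeal/sulcal effusion". The same section says that the BMW "scores ARIA-E (parenchymal vasogenic edema, leptomeningeal/sulcal effusion) according to: extent, location, number of sites involved, radiographic severity". Table 6 of the protocol gives one ARIA-E severity scale, with no separate scales for edema and effusion. Under Section 7.2.1, ARIA-E that the BMW report confirms is entered on the adverse event form and marked as an AESI.

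**SAP, event rule.** Section 6.3.7.1.1: "An event of ARIA-E is defined as an MRI scan where the brain MRI worksheet (BMW) shows the presence of vasogenic edema". Effusion appears neither there nor anywhere else in the SAP.

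**SAP, rules that rest on the event.**
- Severity (6.3.7.1.2): "ARIA-E severity is based on radiographic severity as captured on BMWs".
- Resolution (6.3.7.1.3): "ARIA-E is considered resolved for a participant if all the subsequent MRI scans showed no ARIA-E following the last MRI scan showing ARIA-E".
- Time to first occurrence (6.3.7.1.4): "the number of days from the first dose date to the exam date of the first MRI scan showing ARIA-E".
- Incidence (7.5.7): "Incidence of the first occurrence of ARIA-E within each post-baseline visit will be summarized by radiographic severity for each visit".
- Cross-counts with ARIA-H (7.5.7): "The number and percentage of participants who had a new ARIA-H but did not have an ARIA-E any time post-baseline will be summarized".
- Section 7.5.7 also plans a Kaplan-Meier curve for first ARIA-E, and Section 7.9 plans swim-lane plots of ARIA events for the e4/e4 participants.

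**Precedence and declared changes.** SAP Section 1 lets the SAP prevail over the protocol. SAP Section 9 lists changes to the estimand population, the per-protocol set, physical examinations, the linear mixed-effects analysis, the safety population, and the speech and genetic analyses. It says nothing about ARIA-E. The version history records only that ARIA endpoints were added.

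**The concern.** The protocol names ARIA-E as an identified risk of this drug and makes it an AESI. The two documents give it different content, and the document that prevails is the narrower one.

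A programmer who follows the SAP literally would leave effusion-only scans out of the MRI-based ARIA-E tables. The AESI tables, which come from the BMW report by way of the adverse event form, would keep them. The report could then show two different ARIA-E frequencies for the same trial with no stated reason. For incidence and onset, any error would run in one direction, towards a more favourable safety picture.

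**Working it through.** No figure in the plan is at issue, so the check sets the definitions side by side.

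**Step 1. How the protocol's two findings combine.** Protocol 7.11 joins edema and effusion with the word and. The same sentence lists the three ARIA-H findings in the same way, and the protocol then tracks those three as separate categories, any one of which counts. So the word lists components and does not require both together. ARIA-E under the protocol is edema or effusion or both.

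**Step 2. Classify each possible scan.**

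| Finding on the BMW | Protocol 7.11 | SAP event, read literally | SAP severity source | AESI route |
|---|---|---|---|---|
| Edema only | ARIA-E | Event | BMW grade | AESI |
| Edema and effusion | ARIA-E | Event | BMW grade | AESI |
| Effusion only | ARIA-E | Not an event | BMW grade | AESI |
| Neither | None | None | None | None |

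Only the third row differs. There the SAP also disagrees with itself, since a scan can have an ARIA-E grade without being an ARIA-E event.

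**Step 3. Direction of the effect.** Let E be the scans with edema and F the scans with effusion. The protocol's ARIA-E scans are E ∪ F; the SAP's are E, a subset.
- *Incidence.* A participant with a scan in E also has one in E ∪ F, so the SAP count is equal or lower.
- *First occurrence and Kaplan-Meier.* The earliest date in a subset cannot precede the earliest date in the full set, so onset is equal, later or absent. A participant with effusion only would be censored.
- *Cross-counts.* The total with new ARIA-H does not change, because its rule does not involve ARIA-E. It equals (ARIA-H with ARIA-E) + (ARIA-H without ARIA-E). Any participant who loses ARIA-E status moves from the first group to the second, so the second is equal or higher.
- *Resolution and recurrence.* These are worded in terms of scans showing or not showing ARIA-E, so they take on the same definition, as first occurrence does. A scan with residual effusion after the edema has cleared would count as showing no ARIA-E. The net direction for recurrence is not fixed: an effusion-only return would be missed, while an effusion-only scan between two edema scans would create a resolution and a recurrence.
- *Swim-lane plots for e4/e4.* These show ARIA-E events and inherit the same definition.

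**Step 4. Size.** The effect depends on how many scans fall in the third row and, for participant-level counts, on whether the same participants also had edema. The documents give no ARIA-E counts and no split by component, so no estimate is possible. Zero is within the range.

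**The case against.** The strongest reply is that the wording is shorthand. The BMW form is not in the documents, and nothing shows that it records edema and effusion in separate presence fields. Protocol Table 6 grades by size and number of foci without separating them. With a single ARIA-E field, an edema-only derivation could not be programmed and no count would change. Other signs point the same way. The SAP takes severity straight from the BMW and elsewhere writes simply ARIA-E. It expands the abbreviation with the word edema. The protocol's own example of a missed finding (7.11.1.2) mentions edema and microhemorrhage but not effusion.

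This stands as regards size. It does not settle the wording. For ARIA-H, SAP 6.3.7.2.1 lists all three protocol components; for ARIA-E it lists one of two. A reader could fairly take that as deliberate, and nothing in the SAP says otherwise.

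A second reply is that Section 9 covers changes to methods planned in the protocol, and Protocol 8.3.4 planned only the incidence of MRI safety findings, with no ARIA-E event algorithm. That has some force: the event rule is new, and the version history records that ARIA endpoints were added. But the term itself was defined in Protocol 7.11, and a SAP that takes precedence should say when it uses the term more narrowly.

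A third reply is that nothing is lost, because treatment-emergent AESIs are tabulated and listed and all MRI findings are listed. That is correct. It limits the harm to the MRI summaries and to an unexplained disagreement between tables.

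**Conclusion.** The mismatch is certain on the text; its effect on any count is not. Read literally, SAP 6.3.7.1.1 excludes effusion-only scans that the protocol calls ARIA-E, and every MRI-based ARIA-E summary inherits the exclusion. The direction is fixed for incidence, onset and the cross-counts. The size is unknown and may be zero. An effect requires that effusion-only scans occur, that the BMW data allow them to be told apart, and that the rule is programmed as written.

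Stronger readings are tempting but unsupported:
- A reader might infer that the sponsor chose to narrow the definition. The documents show an unexplained difference, not an intention.
- A reader might infer that ARIA-E will be under-reported. Without the BMW form or any counts, that cannot be said, and AESI reporting is unaffected.
- A reader might infer that participant management is affected. It is not: the protocol's dosing guidance for ARIA uses the central reader's BMW findings, not the SAP's event rule.

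The point is still worth correcting, because the rule concerns an identified risk, can give a wrong safety result as written, and is easy to repair.

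**What to change.** In SAP 6.3.7.1.1, define an ARIA-E event as vasogenic edema and/or leptomeningeal/sulcal effusion on the BMW. State that this definition governs every ARIA-E derivation: incidence, time to first occurrence, the Kaplan-Meier curve, resolution, recurrence, the cross-counts with ARIA-H, and the e4/e4 swim-lane plots. If the BMW has a single ARIA-E field, say that this field defines the event.

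If an edema-only rule is intended, declare it in Section 9 with the reason, and explain there why the MRI and AESI tables may differ.

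The cost is a line of SAP text and, if the BMW fields are separate, a change to the derivation code. The protocol says that the BMW scores both findings, so no new data collection is expected.

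One clerical item can go in the same revision: the MRI visit list in SAP 6.3 omits Week 6, which Table 7-9 includes. The Table 7-9 windows need no change for this point. They decide only which by-visit column a scan falls in, not overall incidence or time to event.
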